In addition, with a sample size of 31 subjects per group, a two-sided type I error rate of 10%, and standard deviation of 7, if the true pattern of mean changes is 4.5, 9.0, and 9.0 for the sham, 2 mA, and 4 mA groups respectively, we would have 83% power to reject the null hypothesis. A 10% type I error rate was selected in consideration of the track record for safety in the intervention, the relative cost of committing a type I and type II error with respect to trial duration, subject utilization, and the remaining need for a subsequently planned Phase III trial should the current trial demonstrate promising results. Based on a conservative estimate from the EXCITE and VECTOR trial^{14, 19}, 8% of subjects are expected to complete less than 10 full sessions of tDCS + mCIMT in the specified 14 day time-window. Thus, the sample size is inflated for the cross-over in treatment effect using an inflation factor of $1/(1-0.08)^2$.¹¹⁷ In addition, up to 15% of subjects may be lost to follow-up prior to collection of the primary outcomes at the 3-month follow-up visit.

Therefore, an inflation of 115% is used to account for the missing samples in the ITT primary analysis. As a result, the final estimated sample size is 43 per group (or 129 subjects in total). Finally, considering the longitudinal nature of the design and adjustment for key covariates, the power will be maintained when using an auto-regressive (1) correlation structure regardless of the degree of correlation between FM-UE scale measured on proximal visits or the strength of the covariates as predictors. We elected not to further reduce the sample size both because a robust estimate of these quantities is not currently available, and to retain sufficient power to evaluate secondary hypotheses.

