9.3 POPULATIONS FOR ANALYSES

- Intent-to-treat (ITT) population

All analyses will be conducted under the ITT principle. That is, the evaluable sample includes all randomized subjects, regardless of whether or not the subjects completed the study protocol; where subjects are classified according to the intervention assignment, they are randomized into.

- Per-protocol (PP) population

Sensitivity of the primary findings will be assessed using a per-protocol sample defined as all subjects who (a) complete at least 8 out of 10 sessions of the intervention; (b) complete the FM-UE scale with all three post-intervention visits; (c) do not experience a recurrent clinical stroke or other pre-specified illness known to impact upper extremity motor functioning during the study period (i.e., Bone fracture in the affected arm, newly diagnosed neuromuscular disease, cervical spine injury.); and (d) do not receive any other forms of rehabilitation therapy after 2 weeks of intervention. The intent of this analysis sample is to assess the maximum possible treatment effect achievable with tDCS at a dose of either 2 mA or 4 mA. It is anticipated that <50% of subjects will receive additional forms of rehabilitation therapy after the 14 day intervention (subjects enrolled in the subacute phase are the ones who have likely received additional rehabilitation therapy), however, if this percentage exceeds 50% the PP sample will exclude criteria (d).

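### The per-protocol criteria run to day 105, so the per-protocol check of the day-15 primary result discards valid day-15 scores

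*Combined protocol and SAP*

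**What the plan says.** Section 9.3 gives the purpose of the sample: "Sensitivity of the primary findings will be assessed using a per-protocol sample". It sets four criteria:

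- (a) at least 8 of the 10 sessions;
- (b) subjects must "complete the FM-UE scale with all three post-intervention visits", which the schedule in section 1.3 places at days 15, 45 and 105;
- (c) subjects "do not experience a recurrent clinical stroke or other pre-specified illness known to impact upper extremity motor functioning during the study period";
- (d) subjects "do not receive any other forms of rehabilitation therapy after 2 weeks of intervention".

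The section adds a rationale: "The intent of this analysis sample is to assess the maximum possible treatment effect achievable with tDCS" at either dose. On (d) it states: "It is anticipated that <50% of subjects will receive additional forms of rehabilitation therapy after the 14 day intervention". If the share passes 50%, (d) is dropped.

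The primary hypothesis (section 9.1) and the primary model estimate (section 9.4.2) are both at day 15. Sections 4.1 and 9.4.1 treat the later visits as follow-up of sustained benefit. Section 9.4 defers details to a separate SAP, which was not in the text reviewed.

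**The concern.** A PP check of a day-15 result should ask whether the result holds among subjects who were treated and assessed as planned up to day 15. Only (a) is confined to that period. As written, a fully treated subject with a valid day-15 FM-UE is excluded for a missed day-105 visit, a fracture at day 60 or outside therapy in week 4. None of these can alter a score already recorded.

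Two things are at stake. One is precision, because usable scores are lost. The other is interpretation. If later attendance or later therapy depends on day-15 response or on arm, the PP comparison is selected on a consequence of the outcome, and a difference between ITT and PP could reflect that rather than adherence. Section 9.3 itself expects the extra therapy mainly in subjects enrolled in the subacute phase, so (d) would also shift the sample away from them.

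**Working it through.** **Timing.** Criterion (d) runs from about day 14 to day 105, which is 91 days. With the assessment no later than day 17, at most 17 − 14 = 3 of those days (3.3%) precede it. If the last session falls on day 12, the figure is 5 of 93 (5.4%). For (c), an assessment on day 13 to 17 of a study period ending on day 95 to 115 leaves between 13/115 = 11% and 17/95 = 18% of the period before the score. These are shares of calendar time, not of events.

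**The plan's own power figure.** Inputs from section 9.2: means 4.5, 9.0 and 9.0, SD 7, two-sided type I error 10%, 31 per arm. The grand mean is 7.5 and the squared deviations sum to 9 + 2.25 + 2.25 = 13.5. The noncentrality is λ = n × 13.5/49, which is 8.54 at n = 31. The noncentral F with 2 and 90 degrees of freedom gives 82.8%, matching the stated 83%.

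**Assumptions for sizing.** The criteria act independently. The full 15% loss in section 9.2 has occurred by day 105. For (a), section 9.2 says "8% of subjects are expected to complete less than 10 full sessions"; since (a) accepts 8 or 9 sessions, 8% is an upper bound for failing it. Nobody fails (c). The share r failing (d) is varied, because the protocol says only that it should be under 50%; the 10% and 30% values are illustrative.

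**PP sample as written:** N = 129 × 0.92 × 0.85 × (1 − r).

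**PP sample tied to day 15:** N = 129 × 0.92 × (1 − L), where L, the loss by day 15, lies between 0 and 0.15.

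Power uses n = N/3 per arm. The half-width of the 90% CI for an arm difference is t(0.95, N − 3) × 7 × √(2/n).

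| PP set | N | Power | Half-width (points) |
|---|---|---|---|
| As written, r = 10% | 90.8 | 82% | 3.0 |
| As written, r = 30% | 70.6 | 72% | 3.4 |
| As written, r = 49.9% | 50.5 | 58% | 4.05 |
| As written, (d) dropped | 100.9 | 86% | 2.8 |
| Tied to day 15, L = 15% | 100.9 | 86% | 2.8 |
| Tied to day 15, L = 0 | 118.7 | 91% | 2.6 |

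If 5% also had other rehabilitation before the day-15 assessment, the day-15 set would be 95.8 to 112.7 subjects (power 84% to 89%).

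**Day-15 scores discarded** among subjects meeting (a): 129 × 0.92 × [(1 − L) − 0.85 × (1 − r)], running from L = 15% to L = 0.

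- r = 10%: 10 to 28 scores (10% to 23.5% of those available)
- r = 30%: 30 to 48 (30% to 40.5%)
- r = 49.9%: 50 to 68 (50% to 57%)

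Criterion (b) alone removes 129 × (1 − L) − 129 × 0.85 subjects who have a day-15 score: 19.4 if all loss comes after day 15, and none if all of it comes before.

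**The 50% rule.** Crossing the threshold moves the sample from about 51 to about 101, on events that mostly follow the primary assessment.

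**The case against.** The strongest counter-argument concerns the model. Section 9.4.2 fits all post-intervention visits and lists arm, baseline FM-UE, time from stroke, visit and site, with no arm-by-visit term. Fitted literally, the arm contrast is shared across visits, so a day-105 score after a fracture or outside therapy would feed the day-15 estimate, and criteria reaching day 105 would protect it. That is fair as far as it goes. The protection needs only the affected later visits to be set aside; the day-15 score can stay. Setting visits aside does change what the later visits contribute, and it relies on those values being missing at random given the model. This should be stated.

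A second argument is that one completer set without outside therapy suits the aim of estimating a maximum effect, the interest in sustained benefit, and the intention in section 2.2 (A.5) to use both ITT and PP analyses to examine the difficulties of subacute enrolment. That supports such a set for days 45 and 105, but does not require dropping day-15 scores from a check of the day-15 result.

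Three limits stand. No decision depends on PP. The discard rates are largely assumed, and the largest need a rehabilitation share just under 50%. The SAP may already define a day-15 set.

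**Conclusion.** The concern holds. Criterion (b) extends to day 105, and most of the time covered by (c) and (d) falls after the assessment they are meant to support. That follows from the text and does not depend on the sizing. Under the stated assumptions the PP sample is about 51 to 91 of 129 for r between just under 50% and 10%, against about 101 to 119 if tied to day 15. The corresponding power is 58% to 82% against 86% to 91%. The power figures are for a simple ANOVA, which section 9.2 describes as more conservative than the planned model.

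Selection bias is possible, but neither its presence nor its direction is shown. ITT remains primary and intact. The consequence is limited to how far the PP result can support or question the primary result. It should still be corrected, because this is the only sensitivity sample for the primary finding named in the text reviewed.

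**What to change.** In section 9.3, define a day-15 PP set as subjects with at least 8 of 10 sessions, an FM-UE score at day 15, and, before the day-15 assessment, no listed illness and no other rehabilitation after the intervention. Drop the 50% rule for this set. Analyse it with the same model as the ITT primary analysis, setting aside visits that follow other rehabilitation or a listed illness, and state the missing-data assumption this makes. If PP results at days 45 and 105 are wanted, apply (b) to (d) up to each visit. Report exclusions by criterion and by arm. ITT stays primary.

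The cost is rewording section 9.3 and the matching SAP text, plus slightly more analysis. No new data are needed, since section 1.3 already schedules concomitant therapy at all three follow-up visits. If the SAP already defines a day-15 PP set, only section 9.3 needs aligning.

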9.4 STATISTICAL ANALYSES

Details of the statistical analyses are provided in the Statistical Analysis Plan.

9.4.1 GENERAL APPROACH

The goal of this proposed phase-2 clinical trial is assessing whether bihemispheric transcranial Direct Current Stimulation (tDCS) at 2 mA or 4 mA, when combined with modified constraint-induced movement therapy (mCIMT) will evoke a motor impairment reduction as measured by the Fugl-Meyer Upper Extremity (FM-UE) scale immediately after the 14 day intervention and at the time of 1 and 3 months follow-up when compared to sham stimulation combined with mCIMT. The central hypothesis is that tDCS, a non-invasive brain stimulation technique, can enhance current post-stroke motor recovery by inducing plasticity and potentiating the brain to be receptive to proven rehabilitation techniques (i.e., mCIMT). However, it is not known whether the current maximum dose (2 mA) is sufficient or whether a higher dose (4 mA) may evoke a better response while maintaining a similar safety and tolerability profile.

9.4.2 ANALYSIS OF THE PRIMARY EFFICACY ENDPOINT(S)

The change in FM-UE Scale in each treatment arm will be modeled using generalized linear mixed effects repeated measures model, where the dependent variable is the change from baseline in

FM-UE to post-intervention visit; the model is adjusted for intervention arm, baseline FM-UE, time from stroke, visit and site; and the primary outcome is the fitted estimate at day 15. Model assumptions, including normality, will be assessed and appropriate transformations will be used in keeping with best practices and conventional approaches in the literature. If the primary null hypothesis is rejected, all pairwise secondary hypotheses will be tested using a Dunnett type multiple comparisons correction^{118, 119}.

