9 STATISTICAL CONSIDERATIONS

9.1 STATISTICAL HYPOTHESES

- Primary Efficacy Endpoint(s):

The primary null hypothesis is that there is no difference in the least-squares mean estimate of the change in FM-UE scale on Day 15 after the initiation of the 14 day intervention among the three dose groups.

$$H_0: \hat{Y}_{sham,15d} = \hat{Y}_{2mA,15d} = \hat{Y}_{4mA,15d}$$

H_A : The means are not all equal

- Secondary Efficacy Endpoint(s):

The secondary null hypothesis is that there is no difference in the least-squares mean estimate of the change in Wolf-Motor Functional Test (WMFT) time score and Stroke Impact Scale (version 3.0, SIS) hand subscale.

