9.2 SAMPLE SIZE DETERMINATION

A change of 4.25-7.25 points on the FM-UE scale is considered to be a meaningful clinically important difference (MCID)¹¹⁶. This study is powered under the assumption that mCIMT alone, will at least achieve this intervention effect (4.5) and furthermore intervention with either 2 mA or 4 mA tDCS will further increase the change in FM-UE scale from the baseline by 4.5 points (i.e., a minimum intervention effect of 9.0). Secondly, based on the meta-analysis of previous trials assessing tDCS in stroke patients³⁹, a conservative estimate of the intervention variability is defined as SD = 7. Based on these assumptions, the current study requires 31 subjects per arm to estimate the 90% confidence interval for the treatment effect in each arm with a standard error of ± 1.3 , assuming an ANOVA-type testing approach which is more conservative than the proposed analysis model which includes multiple time points and adjusts for covariates.

This level of precision was determined to be sufficiently informative to plan a Phase III trial. Specifically, the confidence interval for a clinically meaningful treatment effect will exclude the hypothesized null effect size of 4.5; that is, the estimate and 90% confidence interval for a clinically meaningful treatment might be 9.0 (6.9, 11.1). Moreover, the choice of standard error represents a balance between the level of precision in the estimate and the number of subjects/resources expended during this phase of investigation (**Fig. 9, below**). Further, if the estimate of the standard deviation were overly conservative, the precision of the treatment effect estimate would increase. (N.B. Planning estimates of the null treatment effect size, 4.5, do not impact power as long as the MCID from stimulation remains at 4.5 points.)

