9.4.3 ANALYSIS OF THE SECONDARY ENDPOINT(S)

Aim 1 will also test the secondary null hypotheses that there is no difference in the least-squares mean estimate of the change in Wolf-Motor Functional Test (WMFT) time score and Stroke Impact Scale (SIS, version 3) hand subscale at day 15. The procedure described above will be repeated for each of the secondary endpoints with the type-I error rate adjusted using a Bonferroni type gate-keeping procedure to sequentially test the hierarchical null hypotheses^{120, 121}. That is, if the primary null hypothesis (i.e., no difference in the change in FM-UE Scale between the three groups) is rejected, the secondary null hypothesis of no difference with respect to WMFT time score will be assessed; if that null hypothesis is also rejected, then the null hypothesis of no difference in the SIS hand subscale will be tested.

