9.4.6 SUB-GROUP ANALYSES

In pre-specified subgroup analyses, the primary analysis (§9.4.2) will be repeated but include an interaction effect between sex/gender or race/ethnicity and intervention arm. Differential effects of tDCS by sex/gender or race/ethnicity are not anticipated, and therefore the trial is not powered specifically for these subgroup analyses, but these subgroup analyses will allow any unexpected large variations to be identified and regardless of outcome will assist with planning a Phase III trial which will account for differences if identified here.

Additional analyses are specified in the statistical analysis plan (SAP).

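### The primary model in section 9.4.2 has no arm-by-visit term, so its day-15 arm comparison is an average over days 15, 45 and 105

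*Combined protocol and SAP*

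**What the plan says.** The primary null hypothesis in section 9.1 of the protocol is "no difference in the least-squares mean estimate of the change in FM-UE scale on Day 15" across the three arms. Section 9.4.2 analyses this with a repeated measures mixed model for the FM-UE changes seen after treatment. It gives the terms and the target as follows: "adjusted for intervention arm, baseline FM-UE, time from stroke, visit and site; and the primary outcome is the fitted estimate at day 15". FM-UE is collected after treatment at days 15, 45 and 105 (sections 1.3 and 8.1), so three visits enter the model.

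Section 9.4.3 carries the same model to WMFT and SIS: "The procedure described above will be repeated for each of the secondary endpoints". Section 9.4 adds that "Details of the statistical analyses are provided in the Statistical Analysis Plan". That SAP text is not part of the document reviewed here, so what follows concerns the protocol text.

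**The concern.** With arm and visit as main effects only, visit moves the fitted mean of every arm by the same amount. The fitted difference between any two arms is then identical at all three visits, and evaluating the model at day 15 does not make that difference specific to day 15.

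Two other sections fit this reading, though they do not prove it. Section 9.4.6 names an arm interaction where one is wanted: the subgroup models "include an interaction effect between sex/gender or race/ethnicity and intervention arm". Section 9.2 describes a single-time-point ANOVA as "more conservative than the proposed analysis model which includes multiple time points and adjusts for covariates". With complete data, the extra visits sharpen a day-15 comparison only if the arm effect is pooled over visits.

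A constant effect cannot be taken for granted. The synopsis and section 4.1 leave sustained benefit at days 45 and 105 as something to be assessed, and section 9.3 expects some subjects to receive other rehabilitation after the intervention. At stake is the main test of a dose-selection trial. It controls entry to the pairwise dose comparisons (9.4.2) and to the WMFT and SIS tests (9.4.3).

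**Working it through.** **Inputs from section 9.2:** 31 per arm before inflation, SD 7, two-sided alpha 0.10, mean changes 4.5/9.0/9.0, stated power 83%, AR(1) correlation between visits.

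**Assumptions:** the protocol gives no correlation, so rho is taken from 0.3 to 0.9. SD is 7 at every visit, data are complete, there is no gain from covariates, and both active arms have the same effect.

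**1. The plan's own figure.** The grand mean is 7.5, and the squared deviations sum to 9 + 2.25 + 2.25 = 13.5. The noncentrality is 31 × 13.5 / 49 = 8.54. The noncentral F with 2 and 90 df at alpha 0.10 gives power of 82.8%, which agrees with the stated 83%. The planned power is therefore that of a test at one time point.

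**2. What the additive model estimates.** The generalised least squares weights for a common arm effect are R⁻¹1 / (1′R⁻¹1), where R is the correlation matrix of the three visits. Under AR(1) this becomes (1, 1−rho, 1) / (3−rho). The variance relative to a single visit is k = (1+rho) / (3−rho).

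| rho | weight day 15 | day 45 | day 105 | k |
|---|---|---|---|---|
| 0.3 | 0.37 | 0.26 | 0.37 | 0.481 |
| 0.7 | 0.435 | 0.13 | 0.435 | 0.739 |
| 0.9 | 0.476 | 0.048 | 0.476 | 0.905 |

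Day 105 counts exactly as much as day 15.

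**3. Estimate and rejection rate.** For a pooled difference d, the noncentrality is 31 × (2/3) × d² / (49k). For example, with true differences 4.5/2.25/0 and rho 0.3, d = 0.37 × 4.5 + 0.26 × 2.25 + 0 ≈ 2.25. The noncentrality is 31 × (2/3) × 5.0625 / (49 × 0.4815) = 4.43, and power is 57%.

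| True difference at days 15/45/105 | Estimated as | Rejection, rho 0.3 | rho 0.7 | rho 0.9 |
|---|---|---|---|---|
| 4.5/4.5/4.5 | 4.5 | 98.5% | 92% | 86% |
| 4.5/3.94/3.375 | 3.94 | 95% | 84% | 77% |
| 4.5/3.375/2.25 | 3.375 | 88% | 72% | 64% |
| 4.5/2.25/0 | 2.25 | 57% | 42% | 37% |
| 0/2.25/4.5 | 2.25 | 57% | 42% | 37% |
| 0/1.125/2.25 | 1.125 | 23% | 18% | 17% |

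In the last two rows the day-15 null is true, so the rejection rate should be 10%.

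**4. When power drops below plan.** If the effect falls in equal steps per visit by a total fraction f, then d = 4.5(1 − f/2). Power equals the planned value when (1 − f/2)² = k, so f = 2(1 − √k). This is 61% fading at rho 0.3, 28% at 0.7 and 10% at 0.9. Below those thresholds power is at or above plan, but the estimate is still too small.

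**5. Simulation.** With 4,000 trials per scenario and rho estimated from the data, the additive model at rho 0.3/0.7/0.9 gave 2.26/2.24/2.26 under full fading, with rejection in 57%/41%/37%. With no effect at any visit it rejected in 10%/10%/9%. The day-15 contrast, which with complete data is what the arm-by-visit model gives, kept 82% to 83% power in every constant or fading scenario. It rejected a true day-15 null 9% to 11% of the time.

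**6. Other conditions.** Compound symmetry gives each visit one third of the weight; full fading is again estimated as 2.25, with power of 53% to 36%. With 5/10/15% monotone missing data at the three visits, day 15 carries 39% to 50%, and full fading is estimated as 2.36 to 2.42.

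**The case against.** The algebra is not in dispute; what the protocol specifies is. Section 9.4.2 is a summary without a model equation, and section 9.4 places the details in a SAP that may well contain the term. Several passages point to visit-specific effects. The null in 9.1 carries day-15 subscripts, 9.4.2 picks out a fitted value at day 15, and 9.4.1 wants comparisons with sham at 1 and 3 months, which an additive model cannot separate. The two supporting passages are indirect: subgroup interactions are named because they are themselves the question, and covariate adjustment alone could justify the remark in 9.2. Finally, the largest losses need an effect that vanishes, or that starts late, whereas section 4.1 hypothesises a sustained one.

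Much of this stands. The omission does not prove which analysis will be run, and the size of the harm depends on an unknown correlation and an unknown time course. It also depends on the variances. If the SDs were 7/8/9 and modelled as unequal (an assumption), day 15 would carry 49% to 68% of the weight at rho 0.3 to 0.7, and full fading would be estimated as 2.75 to 3.28. But evidence that a day-15 comparison was intended shows that the listed terms do not deliver it. Two analysts working from 9.4.2 could reach different primary results.

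**Conclusion.** The concern holds for the protocol text. As listed, the model does not estimate the day-15 difference that section 9.1 tests, unless the effect is constant over the three visits. Under the assumptions above, a fading effect is under-estimated, by up to half in the full-fading case. Power in that case is 57% to 37% instead of 83%. With mild fading at low to moderate correlation, power is not lost, although the bias remains. When the arms separate only after day 15, the true day-15 null is rejected 17% to 57% of the time in the two patterns examined, against a nominal 10%. With a constant effect the pooled estimate is unbiased and more powerful, and with no effect at any visit the 10% level holds. Confidence is moderate because the SAP may already include the term. If it does, the protocol's list still has to be brought into line with it.

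**What to change.** In section 9.4.2, add the arm-by-visit interaction with visit as a categorical factor, and define the primary test as the 2-df between-arm contrast at day 15 from that model. State the same for WMFT and SIS in section 9.4.3. Check the SAP and add the term there if it is missing.

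The cost is one sentence in 9.4.2, with the matching statements in 9.4.3 and, if needed, the SAP. The 129 subjects and the 83% power stand, because they were derived for a single time point. The one downside is that, if the effect is truly constant, the pooled model's power of 98.5% to 86% (rho 0.3 to 0.9) is given up for the planned 83%.

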1 PROTOCOL SUMMARY

1.1 SYNOPSIS

Title: TRANScranial direct current stimulation for PPost-stroke motor Recovery- a phase II sTudy (TRANSPORT2)

Study Description: TRANSPORT2 is a phase II multi-center transcranial direct current stimulation (tDCS) dosing selection study based on the preliminary efficacy, safety, tolerability and feasibility.

Objectives: **Primary Objective:** To determine whether there is an overall treatment effect among 3 dosing groups (sham+mCIMT, 2 mA+mCIMT, and 4 mA+mCIMT) on day 15 (\pm 2 days) after the start of the intervention in the Fugl-Meyer Upper-Extremity (FM-UE) scale, a measure of motor impairment. Additional outcome measures include the Wolf-Motor-Function-Test (WMFT), a measure of functional motor activity, and the Stroke-Impact-Scale (SIS), a measure of quality of life. Sustained benefit will be assessed at day 45 (\pm 5 days) and day 105 (\pm 10 days).

Secondary Objectives: To confirm that the proposed intervention is safe (no significant differences in rate of adverse events), tolerable (no significant differences in discomfort as measured by Visual-Analog-Scale), and feasible to administer in a multi-site trial (>80% of subjects complete the treatment protocol and no unexplained/unresolved variability by site).

Exploratory Objectives: To examine whether wCST-LL (structural assessment of integrity of descending motor tract) or MEPs (functional assessment of integrity of descending motor tract) or combination of both are correlated with changes in FM-UE scale, and evaluate the utility of these measures as biomarkers for patient selection criteria in the future confirmatory Phase III study. We also

aim to examine whether structural and functional changes within descending motor tracts correlate with changes in motor impairment and functional motor activity.

Endpoints:

Primary Endpoint: Fugl-Meyer Upper-Extremity (FM-UE) scale a measure of motor impairment;

Secondary Endpoints: Wolf Motor Function Test (WMFT) time score, a measure of functional motor activity; Stroke-Impact-Scale hand subscale as an assessment of patient-centered quality of life.

Study Population:

Subject who is 18-80 years of age of any gender or ethnicity, who had first-ever unihemispheric ischemic stroke in past 30-180 days resulting in unilateral limb weakness with FM-UE ≤ 54 (out of 66) that is stable across two baseline visits at the time of randomization and an mRS ≤ 2 pre-stroke. We are planning to enroll 129 subjects across three arms.

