4 STUDY DESIGN

4.1 OVERALL DESIGN

The **TRANSPORT2 (TRANScranial direct current stimulation current for Post-stroke mOtOr Recovery – a phase II sTudy)** trial will test an **overall hypothesis** that a combination of bihemispheric tDCS stimulation at 2 mA or 4 mA, along with mCIMT, will lead to a greater sustained motor improvement on day 15 (± 2 days) after the start of the intervention as compared to sham stimulation. Sustained benefits will be assessed at day 45 (± 5 days) and day 105 (± 10 days) after the start of the intervention. This multicenter, phase II, sham-controlled 3-arm study will randomize 129 subjects in a 1:1:1 allocation ratio per arm (sham, 2 mA, or 4 mA tDCS), and treat subjects with the assigned dose of tDCS for 30 minutes (± 6) and mCIMT for 120 minutes (± 24) of active time, for 10 sessions over a 14 day period. However, the total time of mCIMT will be less than 150 minutes.

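### Does applying a Dunnett-type correction to all pairwise comparisons in section 9.4.2 undermine the day-15 FM-UE comparisons between arms?

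*Combined protocol and SAP*

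**What the plan says.** Section 9.1 states one primary hypothesis: equal mean change in FM-UE at day 15 across sham, 2 mA and 4 mA. Section 9.4.2 then sets the order of testing: "If the primary null hypothesis is rejected", the pairwise step opens, and "all pairwise secondary hypotheses will be tested using a Dunnett type multiple comparisons correction". It lists no contrasts and names no reference arm. Section 9.4.3 repeats the procedure for the WMFT time score and the SIS hand subscale, in hierarchical order. Section 9.4 leaves statistical detail to a separate Statistical Analysis Plan, whose text is not among the documents reviewed here.

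Other sections point in two directions. Section 4.1 frames the hypothesis for both active doses "as compared to sham stimulation", and section 9.4.1 frames the goal as benefit "when compared to sham stimulation combined with mCIMT". Section 9.4.1 also says "it is not known whether the current maximum dose (2 mA) is sufficient or whether a higher dose (4 mA) may evoke a better response", and the synopsis (section 1.1) calls the trial a "dosing selection study based on the preliminary efficacy, safety, tolerability and feasibility".

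The sizing argument in section 9.2 rests on two things: the precision of a "90% confidence interval for the treatment effect in each arm", and 83% power for the overall test "if the true pattern of mean changes is 4.5, 9.0, and 9.0 for the sham, 2 mA, and 4 mA groups respectively".

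**The concern.** The method and the family do not match. A Dunnett adjustment uses the joint distribution of comparisons with one control, which here means 2 mA and 4 mA each against sham. All pairs would add 4 mA against 2 mA, which is not a comparison with control. A reader can therefore take the sentence in two ways: three contrasts judged against a critical value built for two, or two sham contrasts with the words for all pairs used loosely.

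Three things could be at stake. First, a critical value that is too small for three contrasts could inflate type I error. Second, a dose-selection trial could lack a defined comparison between its two active doses. Third, the correction may be unnecessary after an overall test and so waste power. Because section 9.4.3 repeats the procedure, any defect would carry over to WMFT and SIS hand.

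**Working it through.** **Inputs.** Section 9.2 gives SD 7, two-sided type I error 10%, 31 per arm before inflation, and mean changes 4.5, 9.0 and 9.0. Section 9.4.2 gives the order of testing. The protocol does not state a level for the pairwise tests, so 10% is assumed for them too. The model is the one-way ANOVA that section 9.2 uses for planning.

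**The plan's own figures.** The grand mean is (4.5 + 9.0 + 9.0)/3 = 7.5. The squared deviations sum to 9 + 2.25 + 2.25 = 13.5. The noncentrality is 31 × 13.5/49 = 8.54. With 2 and 90 df the 10% critical F is 2.363, and power is 82.8%, against the stated 83%. For sample size, 31/0.92² = 36.6, and 36.6 × 1.15 = 42.1, rounded up to the stated 43 per arm. Neither figure involves a pairwise correction.

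**Critical values at 31 per arm.** The standard error of a pairwise difference is 7 × √(2/31) = 1.778. The unadjusted two-sided 10% critical t is 1.662, a half-width of 1.662 × 1.778 = 2.95 points. The Dunnett value for two sham contrasts is 1.939, a half-width of 3.45 points and a per-comparison p of about 0.056.

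**Why error is controlled.** With three means, if any two pairwise nulls are true then so is the third, and hence the overall null. The only configurations with a true null are therefore all three arms equal, or exactly one pair equal. In the first, a false pairwise claim requires a false overall rejection, which has probability at most 10%. In the second, only one pairwise test can err, and it is run at 10% or less. Pairwise tests at 10% after overall rejection therefore hold the family-wise error at 10% within FM-UE at day 15. A stricter critical value can only lower it.

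**Simulation** (2,000,000 trials per scenario, 31 per arm, pairwise tests only after overall rejection at 10%):

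| Quantity | Dunnett | Unadjusted 10% |
|---|---|---|
| Family-wise error, all arms equal, three pairs | 9.9% | 10.0% |
| Family-wise error, all arms equal, two sham contrasts | 7.8% | 8.8% |
| False 4 mA vs 2 mA claim, both doses far from sham | 5.6% | 10.0% |
| Each active arm beats sham, means 4.5/9/9 | 70.6% | 75.7% |
| At least one active arm beats sham, 4.5/9/9 | 82.6% | 82.7% |
| Both active arms beat sham, 4.5/9/9 | 58.6% | 68.6% |
| False 4 mA vs 2 mA claim, 4.5/9/9 | 5.5% | 9.8% |

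With all 43 per arm evaluable and fully treated, the power for each active arm is 84.4% against 88.2%. That is a best case, because 43 is 31 inflated for incomplete treatment and loss to follow-up.

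**Effect on secondary endpoints.** As an illustration, suppose the two doses are equal on FM-UE, WMFT and SIS hand, both are far from sham, the endpoints are independent, and 10% carries through. The chance of at least one false dose claim is 1 − 0.9³ = 27% unadjusted and 1 − 0.9445³ = 16% with Dunnett. Positive correlation, or the Bonferroni-type adjustment in section 9.4.3, would reduce both.

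**The case for a change.** The strongest case for changing the text is that contrasts and critical values should be fixed before results are seen. On the protocol wording alone, two competent statisticians could report different sets of comparisons and both claim to have followed it. The Dunnett step is also not needed for error control once the overall test has rejected, and it has a price. Power for each active arm falls by 75.7 − 70.6 = 5.1 points. Power to show that both arms beat sham falls from 68.6% to 58.6%. If only 4 mA works (means 4.5/4.5/9), the share of trials in which the overall test rejects but neither sham contrast is significant rises from about 4.5% to 10.2%.

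The wording point stands as a matter of clarity. It is not an omitted comparison: read literally, 4 mA against 2 mA is one of the pairs, tested after the overall test with the same correction. On the narrower reading, the protocol states no separate hypothesis for that contrast, and section 9.2 plans for equal active arms. Either reading gives a valid analysis, and the separate Statistical Analysis Plan is the natural place to list the contrasts.

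The power figures also stand, but they do not show an error. Section 9.2 promises no pairwise power. What the correction buys is protection against declaring one dose better than the other when they are equal, which matters in a trial meant to choose between them.

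**Conclusion.** No change to the plan is needed. The phrase is imprecise, but under either reading the family-wise error for day-15 FM-UE stays at or below 10%. The 83% power, the 129 subjects and the per-arm interval precision are unaffected.

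Whether to keep the correction is a trade-off on which statisticians can reasonably differ. Removing it gains about 5 points of power per active arm at 31 per arm (about 4 at 43). It nearly doubles false dose claims under the planning pattern, from about 5.5% to 9.8%, gives up simultaneous coverage, and extends to the secondary endpoints. The chance of finding at least one active arm better than sham is practically the same either way.

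This rests on the ANOVA planning model in place of the covariate-adjusted mixed model, on a 10% pairwise level, on sham as the Dunnett control, and on the overall test being applied first, as section 9.4.2 requires.
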